### **7.5.3 Adverse Events of Immunologic Etiology Associated with Pembrolizumab**

Adverse events of an immunologic etiology have been associated with pembrolizumab exposure. These irAE may occur shortly after the first dose or several months after the last dose of pembrolizumab treatment and may affect more than one body system simultaneously. Therefore, early recognition and initiation of treatment is critical to reduce complications. Existing clinical trial data have shown that most irAEs related to pembrolizumab were reversible and could be managed with interruptions of pembrolizumab, administration of corticosteroids, and/or other supportive care. See **Section 6.5.4.3** on medication use for treatment of irAE.

Depending on the severity of the irAE, pembrolizumab will be temporarily withheld or permanently discontinued. In general, for an irAE requiring dose interruptions, low-dose dexamethasone ( $\leq 4\text{mg/day}$ ) should be initiated and tapered when the irAE is  $\leq$  Grade 1.

For a life-threatening irAE, IV dexamethasone should be initiated first followed by oral steroids. Other immunosuppressive treatment should also be initiated if the irAEs cannot be controlled by corticosteroids alone.

The next doses(s) of pembrolizumab will be withheld until the irAE has been reduced to  $\leq$  Grade 1 and dexamethasone dose has been tapered to  $\leq$  4mg/day and/or discontinued.

Pembrolizumab should be permanently discontinued if the irAE does not resolve within 12 weeks of last dose or dexamethasone cannot be reduced to  $\leq$  4 mg/day within 12 weeks.

- With regard to events  $\geq$  Grade 2 related to PTE or CE (eg, hemiparesis, seizure), pembrolizumab treatment should be held until those events resolve to  $\leq$  Grade 1. Pembrolizumab should be permanently discontinued for Grade 4 PTE or CE and/or events  $\geq$  Grade 3 related to PTE or CE.

**Refer to the most recent Keytruda® (pembrolizumab) package insert and “Guide for Keytruda®” for a list of adverse reactions for which pembrolizumab should be interrupted or permanently discontinued along with recommended management. This may include but not be limited to the following:**

- Immune-mediated pneumonitis: Withhold for moderate, and permanently discontinue for severe, life-threatening or recurrent moderate pneumonitis.
- Immune-mediated colitis: Withhold for moderate or severe, and permanently discontinue for life-threatening colitis.
- Immune-mediated hepatitis: Monitor for changes in hepatic function. Based on severity of liver enzyme elevations, withhold or discontinue pembrolizumab. Consider corticosteroid therapy.
- Immune-mediated endocrinopathies:
  - Adrenal insufficiency: Withhold for moderate and withhold or permanently discontinue for severe or life-threatening adrenal insufficiency.
  - Hypophysitis: Withhold for moderate and withhold or permanently discontinue for severe or life-threatening hypophysitis.
  - Thyroid disorders: Monitor for changes in thyroid function. Withhold or permanently discontinue for severe or life-threatening hyperthyroidism.
  - Type 1 diabetes mellitus: Monitor for hyperglycemia. Withhold pembrolizumab in cases of severe hyperglycemia.
- Immune-mediated nephritis: Monitor for changes in renal function. Withhold for moderate, and permanently discontinue for severe or life-threatening nephritis.
- Immune-mediated skin adverse reactions including Stevens- Johnson syndrome (SJS) and toxic epidermal necrolysis (TEN): Withhold for severe and permanently discontinue for life-threatening skin reactions.
- Other immune-mediated adverse reactions: In organ transplant recipients, consider the benefit of treatment with pembrolizumab versus the risk of possible organ rejection.

In addition, pembrolizumab can cause severe or life-threatening infusion-related reactions, including hypersensitivity and anaphylaxis. During infusion, monitor patients for signs and symptoms of infusion-related reactions including rigors, chills, wheezing, pruritus, flushing, rash, hypotension, hypoxemia, and fever. For severe (Grade 3) or life-threatening (Grade 4) infusion-related reactions, stop infusion and permanently discontinue pembrolizumab. Follow the recommended management practices noted above, in the current pembrolizumab package insert, or in keeping with current medical practices when managing reactions noted during or after pembrolizumab infusion.

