Patients receiving PVSRIPO only will be followed according to the schedule of assessments with MRI and required visits occurring approximately every 9 weeks after Week 11.

After the first pembrolizumab treatment, subsequent pembrolizumab treatments will occur every 3 weeks ( $\pm 1$  week) thereafter, up to Week 104 (24 months). Treatment with pembrolizumab may be interrupted and/or discontinued for irAE, as specified in [Section 7.5.3](#) and discontinued for confirmed PD. NOTE: If pembrolizumab is permanently discontinued, then safety laboratory evaluations that are not SOC are no longer required after 30 days from the date of pembrolizumab discontinuation.

If this visit is required due to delayed pembrolizumab treatment at Week 2, the following assessments at Week 3 to Week 4 should occur (prior to the first dose of pembrolizumab, as applicable):

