## Planned Treatment:

- Pembrolizumab (200 mg IV) treatment is planned to occur every 3 weeks up to a maximum of Week 104 (24 months).
  - Patients who remain on pembrolizumab will report for infusions every 3 weeks. If pembrolizumab is permanently discontinued, then safety laboratory evaluations that are not SOC are no longer required after 30 days from the date of pembrolizumab discontinuation. See **Sections 5.5** and **5.6** for patients who permanently discontinue or interrupt pembrolizumab treatment before and after study Week 11.
- In general, patients who discontinue pembrolizumab treatment and/or are no longer in the per protocol population (ie, have initiated non-study tumor treatments; see **Section 8**) should be followed per SOC, as possible/feasible.
- If approved by Sponsor or designee, patients with confirmed progression meeting the key safety and infusion related eligibility criteria may be eligible for retreatment with PVSRIPO,  $\geq$  3 weeks after their last pembrolizumab treatment under this protocol.
  - Treatment with pembrolizumab or other treatments after PVSRIPO retreatment will be at the discretion of the investigator and will be recorded in the eCRF.

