## **5.5 Follow-Up Period of Off Study Participants/Patients Permanently Discontinuing Pembrolizumab**

If a patient permanently discontinues pembrolizumab prior to or at Week 11, they should report to the clinic as scheduled for follow-up as noted in **Table 1**.

Patients who no longer meet the criteria for the per protocol population (see **Section 8**) or patients who permanently discontinue pembrolizumab for confirmed progression or irAE requiring permanent discontinuation after Week 11 will remain in follow-up, where assessments will occur as outlined in the SOA noted in **Table 1**. However, the frequency should occur per SOC (ie, approximately every 9 weeks), as feasible.

Entry of all applicable data and uploading of scans should occur no later than every 3 months. If SOC follow-up occurs less frequently (ie, greater than 3 months between visits/phone call), data should be transmitted within 2 weeks ( $\pm$  1 week) of acquisition.

Data to be entered in the eCRF during this period may include, but is not limited to the following:

- Patient status: deceased or alive
- Use of additional anti-cancer therapies and/or concomitant medications used to manage PVSRIPO-related inflammation (ie, corticosteroids, bevacizumab) and/or adjustments to such therapies since the last entry.
  - Entries should include start/stop date, dose, route, and frequency.
- MRIs conducted per SOC
  - Any SOC MRIs (deidentified) may be requested by the Sponsor or Sponsor designee. For all SOC MRI, the assessment of tumor size, volume, and other characteristics should be recorded on the eCRF no less than every 6 months as well as in the event of disease progression.
- Neurosurgical procedures required for reasons other than tumor progression (ie, for managing hydrocephalus) since last visit and details of these procedure(s).

Results of any molecular, genetic, or histologic testing from all biopsies/tissue obtained since last recorded entry.

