## 7 Safety and Pharmacovigilance

The Investigator is responsible for the identification and documentation and reporting of AEs and SAEs, as provided in this protocol. During each study visit and other patient contacts (eg, phone contact, telemedicine visit), the Investigator or designated study personnel must assess, through non-suggestive inquiries of the patient or evaluation of study assessments, whether an AE or SAE has occurred. In addition, if the Investigator (or designee) receives a report from other health care providers or legally authorized representatives that is suggestive of an AE/SAE in the study patient, the Investigator must similarly follow up for reporting purposes.

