### **7.1.3 Treatment Emergent Adverse Events**

Treatment emergent AEs will be noted from the time of PVSRIPO infusion through the time the patient comes off study/no longer meets the requirements for the per protocol population (as defined in **Section 8**) and 30 days thereafter. Any AEs related to the catheter placement without PVSRIPO infusion will be summarized separately (eg, patient withdraws due to AE experienced after catheter placement but before PVSRIPO infusion).

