## **7.2 Serious Adverse Events**

An SAE is any AE meeting the following criteria:

Death	An AE that results in death (note: death due to progression is not an AE/SAE but should be reported as noted in the eCRF completion guidelines).
-------	--

Life-threatening AE	An AE that places the participant, in the view of the Investigator, at immediate risk of death from the AE as it occurred (ie, does not include an AE that had it occurred in a more severe form, might have caused death).
Required or prolonged participant hospitalization	An AE that results in an initial participant hospitalization or prolongs an existing hospitalization of the participant. If a participant is hospitalized as part of the clinical use of the study treatment, the period of normal hospitalization will be based on the Investigator's judgement and experience. Hospitalizations longer than this period will be considered prolonged hospitalizations.
Persistent or significant disability/incapacity	An AE that results in a substantial disruption of a participant's ability to conduct normal life functions.
Congenital anomaly/birth defect	A congenital anomaly/birth defect that occurs in the offspring of a participant exposed to the study drug.
Important medical event	An AE that may not result in death, be life-threatening, or require hospitalization may be considered an SAE when, based upon appropriate medical judgment, the event may jeopardize the participant and may require medical or surgical intervention to prevent 1 of the outcomes listed above. Examples of such "important medical events" include allergic bronchospasm requiring intensive treatment in an emergency room or at home, blood dyscrasias or convulsions that do not result in participant hospitalization, or the development of drug dependency or drug abuse

SAEs must be reported by the Investigator to the Sponsor or designee within 24 h of discovery for all patients from the time of consent, while on study and for 30 days after 1) completion of study participation or 2) if patient is rendered off-study and in the follow-up period only. SAEs will be reported in the eCRF with instruction provided in the eCRF Completion Guidelines.

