## 8 Statistical Analyses

This single-arm study is designed to evaluate the efficacy, safety and tolerability of PVSRIPO when followed by pembrolizumab treatment in patients with rGBM. Summary statistics (eg, n, %, CI) will be employed to describe the key findings (ORR, DOR, incidence and severity of DLT, Grade 3 or higher AE, etc.).

Adverse events considered related to screening or other pre-infusion procedures that are not standard of care (eg, PV booster, biopsy prior to infusion, catheter placement without PVSRIPO infusion) will be summarized separately from TEAE (after PVSRIPO infusion), as will data from patients receiving only PVSRIPO and not at least one dose of pembrolizumab. The number of doses of pembrolizumab received and other baseline characteristics will also be explored as variables for safety and efficacy (eg, age, number of prior recurrences, baseline NANO and KPS, extent of prior resection, prior bevacizumab and chemotherapy use, tumor genetic profile).

All patients enrolled and treated with PVSRIPO will be summarized in all analyses. In addition, a per-protocol analysis will also explore the impact of excluding patients meeting pre-defined criteria from radiographic and survival analyses as outlined in [Section 8.4.6](#). For comparisons of efficacy or safety relative to PVSRIPO alone or pembrolizumab alone from other data sources, both the overall and per-protocol populations may be considered.

In general, patients should follow the protocol treatment plan outlined and will be considered on study if there are no major protocol deviations including prohibited tumor-treatments, until the time of confirmed disease progression, or until the investigator and/or patient feel it is in the patient's best interest to stop study treatments or study participation.

The SAP, which will be finalized before conducting the analyses, will present details about planned statistical summary methods and analyses. A brief summary of the SAP is provided below by section. The SAP will govern in the event the protocol and the SAP differ.

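### Explicit rules close new adverse event collection 30 days after a patient goes off study or leaves the per-protocol set, although the protocol expects immune-related events months after the last pembrolizumab dose and other sections imply continued collection

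*Protocol*

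**What the plan says.** Protocol Section 7.5.3 describes the timing of irAEs on pembrolizumab: "These irAE may occur shortly after the first dose or several months after the last dose of pembrolizumab treatment".

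Two rules fix when collection of new events stops:
- Section 7.1.3: treatment-emergent events (TEAEs) are noted from PVSRIPO infusion "through the time the patient comes off study/no longer meets the requirements for the per protocol population", plus 30 days.
- Section 7.2: reporting of serious events (SAEs) begins at consent. Its end is set thus: "for 30 days after 1) completion of study participation or 2) if patient is rendered off-study and in the follow-up period only".

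Section 8 says when a patient leaves the study. Patients "will be considered on study if there are no major protocol deviations including prohibited tumor-treatments, until the time of confirmed disease progression". A decision by the investigator or the patient to stop also ends on-study status. Section 5.3.1 also stops pembrolizumab at confirmed progression. Section 5.3.4 explains loss of per-protocol status narrowly: "no longer in the per protocol population (ie, have initiated non-study tumor treatments". The exclusion list in Section 8.4.6 is much longer.

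Other text points towards continued collection:
- Section 7: "During each study visit and other patient contacts (eg, phone contact, telemedicine visit), the Investigator or designated study personnel must assess" whether an AE or SAE has occurred.
- Table 1: the adverse event row is continuous, with no end stated.
- Section 5.5: follow-up assessments are those of Table 1, although "the frequency should occur per SOC (ie, approximately every 9 weeks), as feasible". Its list of data to enter does not name adverse events but is expressly not exhaustive.
- Section 5.4: all treated patients are expected to stay in long-term follow-up, and this is the default.

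SAP Section 3.2.6 defines a TEAE by its start (on or after catheter placement) and sets no 30-day limit. SAP Table 14.3.1.10 tabulates irAEs.

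**The concern.** The protocol recognises a late-onset risk and then, on its explicit rules, stops looking for new events early. Frequency and severity of TEAEs in patients who received the combination is the primary safety endpoint. The SAP would count a late irAE if it were in the database, so any loss happens at collection and cannot be repaired in the analysis.

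The direction is under-counting of late, new-onset irAEs. There is also a consistency problem. A site that follows Sections 7.1.3 and 7.2 and a site that follows Section 7 and Table 1 would collect different data from similar patients, and the pooled table would not show which rule each had used.

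The per-protocol trigger raises a separate difficulty. It ties the end of safety collection to membership of an efficacy analysis set.

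**Working it through.** The 30 days is a fixed rule, so there is no derived figure to reproduce. The check is calendar arithmetic followed by a comparison of texts.

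**Inputs**
- Dosing: Section 5.3.1, "subsequent pembrolizumab treatments will occur every 3 weeks", with a window of 1 week either way, so doses are 14 to 28 days apart.
- Off-study date: confirmed progression (Section 8), taken as the date of confirmation.
- Collection tail: 30 days (Sections 7.1.3 and 7.2).
- Longest irAE hold before permanent discontinuation: 12 weeks from the last dose (Section 7.5.3), or 12 × 7 = 84 days.
- Follow-up contacts after Week 11: about every 9 weeks (Section 5.5), or 9 × 7 = 63 days.

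**Closing date.** Days from last dose to end of collection = days from last dose to off-study + 30.
- Progression confirmed on the day of a dose: 0 + 30 = 30 days.
- Just before the next dose at 3 weeks: 21 + 30 = 51 days.
- Just before the next dose at 4 weeks: 28 + 30 = 58 days.
- Windows of 7 days applied to nominal visit dates, early then late: 35 + 30 = 65 days.
- After a full 12-week hold: 84 + 30 = 114 days.

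**Against the stated risk.** The documents do not define the late-onset period, so any number for it is an assumption. At 30.5 days per month, two months is 61 days and three months is 91.5 days. The on-schedule range of 30 to 58 days ends before either. The 65-day case just passes two months. The 114-day case reaches 114 / 30.5 = 3.7 months.

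**Next routine contact.** After Week 11 it falls about 63 − 30 = 33 days after collection has closed under the 30-day rules.

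**Does other text cover the gap?**
- The Synopsis (pembrolizumab discontinuation) and Section 7.1 follow events already open to an outcome. They do not deal with new onset.
- Section 7.2 keeps an untimed route for death, congenital abnormality and events of grave concern, if they come to the investigator's attention and are linked to the study.
- Section 7.6 requires the sponsor to report serious, unexpected events associated with study drug, with no 30-day limit.
- Neither of these two routes actively collects a new, expected, non-grave irAE.
- Table 1, footnote 18, also drops safety laboratory tests outside standard of care 30 days after pembrolizumab stops, so later laboratory-detected irAEs depend on routine care.

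**The per-protocol trigger**
- Section 8.4.6 says the set is identified before database lock, so a site cannot apply it reliably during follow-up.
- The same section excludes patients given more than 4 mg/day dexamethasone for more than 14 days after the first pembrolizumab treatment. Read literally, an irAE needing prolonged steroids can itself start the 30-day clock. The gloss in Section 5.3.4 is narrower, so sites face two readings.
- SAP Section 6 drops the per-protocol analysis, so the trigger serves no planned analysis.

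**The case against.** The strongest reply is that the plan already collects these events. Section 5.4 keeps all treated patients in follow-up whatever they stop or add, Section 5.5 refers follow-up to Table 1, Table 1 shows adverse events as continuous, and Section 7 requires inquiry at every contact. Section 8 introduces its on-study definition as a general statement only. Much of this stands: it makes the position a conflict rather than a clear early stop. It does not remove the conflict, because Section 7.2 expressly covers the patient who is off study and in follow-up only, and Section 7.1.3 adds the per-protocol stop.

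A second reply is that Section 7.5.3 is clinical background urging early recognition and sets no collection period, and that how long to collect after progression is a design choice. That is fair. It still leaves the stated risk and the explicit rules unreconciled.

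A reader might go further and infer that new irAEs are certainly lost at every follow-up contact from progression to Week 104. The documents do not support this. It assumes that the 30-day rules override Section 7 and Table 1, and that patients live to Week 104, whereas Section 1 puts median survival in recurrent disease at 6 to 10 months. Nor do the documents support a precise share of the late-onset period missed: they give no onset distribution, and dose holds move the closing date. Patients who stop pembrolizumab but still count as on study and per-protocol remain covered.

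**Conclusion.** The concern holds as a conflict between sections with a one-sided risk. Under the explicit rules, collection of new events closes about 30 to 58 days after the last dose for a patient dosed on schedule who stops at confirmed progression, and up to about 114 days after a full irAE hold. Sites that apply those rules would miss new-onset, mainly non-grave irAEs in off-study patients; grave or serious unexpected events keep a passive route. The range assumes that off-study is dated at confirmation, not at the back-dated first observation that Table 3 uses as the progression date, and that per-protocol status was not lost earlier.

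The number of events lost cannot be computed, and short survival limits it. The per-protocol trigger is unsound whichever section governs. This should be corrected, but it does not invalidate the safety analysis.

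**What to change.** - **Section 7.1.3:** delete loss of per-protocol status as a reason to stop TEAE collection.
- **Sections 7.1.3, 7.2 and 5.5:** for patients who received pembrolizumab and remain in follow-up, record new irAEs and SAEs at the existing contacts, about every 9 weeks, through the planned follow-up and regardless of on-study status. Name both in the Section 5.5 data list so that it agrees with Section 7 and Table 1.
- **SAP Table 14.3.1.10:** report irAE onset relative to the last pembrolizumab dose, and flag events that begin after subsequent anticancer therapy.

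No new visits or tests are needed. The cost is a protocol amendment with IRB approval, probably small eCRF changes, and extra adverse event entry. Some late events will be confounded by later therapy, which the flag makes visible. The gain is small for patients dosed to near Week 104, whose follow-up ends soon afterwards, and for those who accept only vital-status and routine MRI follow-up. SAP Section 6 records that enrollment fell short of plan, so an amendment may help fewer patients; the SAP change is useful in any case.

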## **7.6 Notification for Serious or Unexpected Adverse Events**

The investigator, or responsible person per local requirements, must comply with the applicable local regulatory requirements related to the reports of SAEs to regulatory authorities and the IRB/ IEC.

The Sponsor is responsible for appropriate reporting of SAEs to the necessary regulatory bodies where appropriate. The Sponsor will report to the Investigators all suspected unexpected serious adverse reactions (SUSARs) associated with PVSRIPO/PVSRIPO followed by pembrolizumab use. The Investigator (or Sponsor where required) must report any SUSARs to the IRB/IEC according to the Institution's regulations.

The Sponsor is responsible for the ongoing evaluation of the study drug. Any adverse experience associated with the use of the study drug that is both serious and unexpected must be reported. In accordance with the US Code of Federal Regulations, Title 21 CFR Part 312.32, and the International Conference on Harmonization (ICH) Guidelines for Clinical Safety Data Management Definitions and Standards for Expedited Reporting, the Sponsor must submit written documentation in the form of an IND Safety Report or SUSAR reports, respectively. All events qualifying as IND Safety Reports/SUSARs will be reported to the IRB/IECs. IND Safety Reports/SUSARs are required to be reported within 7 calendar days for life-threatening events and those resulting in death or 15 calendar days for all others. These timeframes begin with the first notification of the IND Safety Reports/SUSARs to the drug safety group from the Investigator.

The Sponsor should submit to the regulatory authority all safety updates and periodic reports, as required by applicable regulatory requirements.

